3.0 PROTOCOL SUMMARY

Sponsor	Merck & Co., Inc.
Protocol Title	A prospective digital quality improvement project to apply best clinical practices to patients at high risk of respiratory complications
Drugs	The following FDA cleared drugs will be used in this study: 
 • Sugammadex
Study Objectives	Primary Objective 
 1) Time to “fitness for discharge” from the recovery room, as noted by the time the anesthesiologist places the discharge order, before and after intervention.

	
2) Incidence of hypoxemia in the PACU before and after intervention as defined by documentation oxygen saturation below 90%
 
Secondary Objectives
 
 1) Performance of identified best practices before and after intervention. 2) Incidence of hypoxemia in the PACU before and after intervention as defined by documentation of oxygen saturation below 95% 3) The duration of supplemental oxygen needed by high risk patients before and after intervention 4) Postoperative reintubation rate 5) Unplanned upgrade of care (defined as patients who are sent to the ICU after being admitted to a regular ward)
Study Design	Historical prospective comparative effectiveness trial
Study Phases	
Retrospective Data Analysis
 
Perform a retrospective analysis on data contained in our data warehouse on the incidence of respiratory dysfunction in the post-operative care unit (PACU) before and after the introduction of sugammadex into clinical practice.
 
Respiratory depression pathway implementation
 
Develop and implement a clinical best practice pathway designed to prevent postoperative respiratory complications in higher risk patients (such as those with OSA or preexisting respiratory disease) using education and clinical decision support in patients.

Sample Size	~13,000 retrospective and ~6,500 prospective
Clinical Sites	Ronald Reagan UCLA Medical Center, UCLA Santa Monica Hospital
Study Population	RRUMC or UCLA Santa Monica patients aged 18 and older who had a general anesthetic with either rocuronium or vecuronium.
Inclusion Criteria	
One or more:
 
 • Obstructive or restrictive lung disease in EMR • OSA • Preoperative O2 sat <95% (avg/median of 12 hours before surgery) • BMI > 40 • Acute respiratory infection within 1 month prior to surgery

[figure not shown]

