10.0 STUDY ENDPOINTSVariables/Time Points of Interest

- 1) **PACU Discharge Time (primary endpoint):** The duration in minutes from patient arrival in PACU until the ready for discharge order is placed by the anesthesiologist. This captures the time until they are clinically ready for discharge and eliminates noise such as the availability of beds that might effect actual discharge time
- 2) **Incidence of oxygen saturation <90%:** A binary variable indicating if the patient had any oxygen saturations below 90% from arrival in PACU until being marked for discharge
- 3) **Incidence of oxygen saturation <95%:** A binary variable indicating if the patient had any oxygen saturations below 95% from arrival in PACU until being marked for discharge
- 4) **Duration of supplemental oxygen use in PACU:** The total time in minutes that a patient received supplemental oxygen from arrival in PACU until being marked for discharge
- 5) **Reintubation rate:** The incidence of patients who required reinsertion of an endotracheal tube after the patient was extubated in the OR. This includes patients who were reintubated in the PACU or subsequently after PACU discharge.
- 6) **Unplanned Upgrade of Care:** The incidence, defined as a binary variable, of patients who were transferred to an ICU after being admitted to a non-ICU setting.
- 7) **Obstructive Sleep Apnea (OSA):** The presence of obstructive sleep apnea based upon previous structured data in the electronic medical record (EMR) such as prescriptions for CPAP, medical history and the anesthesiologist's preoperative note.

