25.0 POWER ANALYSIS AND SAMPLE SIZE DETERMINATION

25.1 Retrospective analysis

In order to assess the change in time to readiness for PACU discharge and postoperative respiratory dysfunction (duration of oxygen saturation below 90%) after the introduction of sugammadex we will construct two models. First, we will utilize propensity score matching (PSM)¹⁴ to adequately risk balance the patients pre/post sugammadex introduction (variables mentioned in section 2.4). We will use the nearest-neighbor PSM approach and start with a caliper of width equal to 0.2 of the standard deviation of the logit of the propensity score (as described by Austin¹⁵). We will assess balance of the covariates pre/post intervention by computing

standardized mean differences (SMD) for each variable and will use the rule of thumb “SMD less than 0.1”¹⁶ to indicate adequate balance. Finally, we will also construct a table of patient characteristics pre/post matching to see how well the algorithm balanced the patients. If individual covariates are not adequately balanced with the default propensity score matching algorithm, we will try different matching parameters until adequate balance is achieved (e.g. change the caliper size for what we consider a match and/or run a more advanced propensity score model including interaction or squared terms).

After adequate balance is observed, we will compare our outcomes of interest between pre/post periods using a linear (or log-linear) model for time to readiness and logistic regression for our binary outcome (postoperative respiratory dysfunction) using the propensity matched dataset. An interrupted time-series (also known as segmented regression) analysis as described by Wagner¹⁷ will be conducted for each outcome to estimate the pre-intervention time trend, immediate impact of intervention (change-point), as well as reliably estimating the slope change after the intervention. All estimates of interest from these models will be summarized with p-values and 95% confidence intervals.

Statistical analyses will be performed using R V3.5.1 (Vienna, AU) using the “*Match*” package for propensity score matching and p-values <0.025 (for our two primary outcomes) will be considered statistically significant utilizing the Bonferroni adjustment (0.05/2).

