At this point, we estimate that the pathway will recommend sugammadex for all patients in the medium or high-risk groups as well as some patients in the low risk group (i.e. those patients requiring deep neuromuscular blockade to facilitate surgical conditions such as robotic procedures, free flap cases and others). Given the large number of patients, Merck would supply one vial of study drug for each patient. Thus the total amount of study drug would be no more than 6,500 patients for the one year intervention time.

Given 1 year of data, we observed an overall average PACU discharge time of 152.54 minutes (SD=623.86). With one year of post-data, we are adequately powered (90%) to pick up a reduction in PACU discharge time as small as 27.04 (two-sample t-test, alpha=0.025). Since the current difference in PACU discharge time between low and high risk groups is 67.52 (subtracting 216.62-149.10, see table), we feel the 27.04 minimally detectable difference gives us a great chance of detecting a meaningful difference.

Given 1 year of data (pre-period), we observed the rate of patients with any time SpO2<90% was 4.6% (574/12,467). With one year of post-data, we are adequately powered (90%) to pick up a reduction in this rate if it decreases to around 3.7% in the post (chi-square test, alpha=0.025). Since the current difference in patients with any time with SpO2<90% between low and high risk patients is 5.2% (subtracting 9.2%-4.0%), we feel the minimally detectable difference of 3.7% (4.6%-3.8%) is feasible.

Table 2.

	suppl O2, mean (SD)	PACU disch. Time, mean (SD)	Reintubation, freq (%)	Unplanned upgrade, freq (%)	SpO2<90%, freq (%)	SpO2<95%, freq (%)
OVERALL(n=13,277)	74.81 (241.82)	152.54 (623.86)	89 (0.7%)	138 (1.0%)	574 (4.6%)	6510 (52.3%)
low (n=9,841)	74.48 (280.55)	149.10 (599.78)	63 (0.6%)	111 (1.1%)	372 (4.0%)	4603 (50.0%)
medium(n=2,997)	74.98 (95.67)	154.43 (536.58)	23 (0.8%)	22 (0.7%)	164 (5.8%)	1658 (58.8%)
high (n=439)	79.54 (88.44)	216.62 (1321.46)	3 (0.7%)	5 (1.1%)	38 (9.2%)	249 (60.9%)
Smallest detectable difference (90% power)	9.61	24.84	0.4%	0.4%	3.8%	50.3%

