- Preexisting respiratory disease: The presence of obstructive or restrictive lung disease as defined based on the structured data in the EMR such as previous PFT results, previous medication and previous diagnoses. For analysis purposes patients will be divided into low, medium and high risk groups based on the extent of their disease.

Statistical Methods:

All analysis will be performed by the study team at UCLA.

Retrospective analysis: In order to assess the change in time to readiness for PACU discharge and postoperative respiratory dysfunction (duration of oxygen saturation below 90%) after the introduction of sugammadex we will construct two models. First, we will utilize propensity score matching (PSM) to adequately risk balance the patients pre/post sugammadex introduction. We will use the nearest-neighbor PSM approach and start with a caliper of width equal to 0.2 of the standard deviation of the logit of the propensity score. We will assess balance of the covariates pre/post intervention by computing standardized mean differences (SMD) for each variable and will use the rule of thumb “SMD less than 0.1” to indicate adequate balance. Finally, we will also construct a table of patient characteristics pre/post matching to see how well the algorithm balanced the patients. After adequate balance is observed, we will compare our outcomes of interest between pre/post periods using a linear (or log-linear) model for time to readiness and logistic regression for our binary outcome (postoperative respiratory dysfunction) using the propensity matched dataset. An interrupted time-series (also known as segmented regression) analysis as described by Wagner will be conducted for each outcome to estimate the pre-intervention time trend, immediate impact of intervention (change-point), as well as reliably estimating the slope change after the intervention. All estimates of interest from these models will be summarized with p-values and 95% confidence intervals.

Statistical analyses will be performed using R V3.5.1 (Vienna, AU) using the “Match” package for propensity score matching and p-values <0.05 will be considered statistically significant.

Prospective analysis: The prospective analysis will largely follow a similar framework however we will focus on the primary and secondary outcomes as described above and will use a one year period prior to implementation as our baseline.

Power/Sample Size:

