Sugammadex was introduced into clinical practice at UCLA in May of 2016, thus we have well more than one year of data prior to and after sugammadex introduction. As a result, the power analysis and sample size discussion is roughly the same for the retrospective and prospective portions of this study.

Over the previous one year period, approximately 6,5000 patients received general anesthesia with the use of either rocuronium or vecuronium. Given that our surgical volumes are stable we would expect the sample size for the prospective portion of our study to be roughly the same. The table below contains the risk stratification for this group.

To determine the study power, we analyzed the incidence of the primary and secondary outcomes for our historical population. Because there is no current pathway, we are unable to explicitly model the power

for pathway compliance, however the power for the primary outcome as well as secondary outcomes were calculated.

In order to determine our power for the study variables patients were separated into low, medium, and high-risk groups. Low risk patients were those who had no prior documentation of OSA or respiratory disease prior to surgery. Medium risk patients were those with either OSA or respiratory disease and high risk patients were those with both diseases. It is important to note that this classification is significantly simplified as compared to the analysis that will be performed for either the retrospective or prospective studies as it fails to account for key factors such as severity of illness. Nonetheless we believe that these simplifications have the effect of underestimating the potential power and thus the below serves as a conservative estimate.

Given 1 year of data, we observed an overall average PACU discharge time of 152.54 minutes (SD=623.86). With one year of post-data, we are adequately powered (90%) to pick up a reduction in PACU discharge time as small as 24.84 (two-sample t-test, alpha=0.05). Since the current difference in PACU discharge time between low and high risk groups is 67.52 (subtracting 216.62

149.10, see table), we feel the 24.84 minimally detectable difference gives us a great chance of detecting a meaningful difference.

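### If both primary outcomes stay, Holm's procedure would improve cheaply on the protocol's fixed Bonferroni split and would validly replace the SAP's unadjusted 0.05

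*Combined protocol and SAP*

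**What the plan says.** **Decision rule.** Protocol 25.1 (Retrospective analysis) says "p-values <0.025 (for our two primary outcomes) will be considered statistically significant utilizing the Bonferroni adjustment (0.05/2". SAP, Statistical Methods, says "p-values <0.05 will be considered statistically significant" and makes no adjustment. Protocol 25.2 and the matching SAP paragraph carry the approach to the prospective phase only as a broadly similar framework and give no threshold.

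**Power statements.** Each document is sized at its own threshold. Protocol 26.0 claims 90% power "to pick up a reduction in PACU discharge time as small as 27.04 (two-sample t-test, alpha=0.025" and, for SpO2 below 90%, a fall from 4.6% to about 3.7% at alpha 0.025. SAP, Power/Sample Size, claims 90% power "to pick up a reduction in PACU discharge time as small as 24.84 (two-sample t-test, alpha=0.05" and a fall to about 3.8% at alpha 0.05. The last row of protocol Table 2 still prints the 0.05 figures, 24.84 and 3.8%.

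**Primary family.** Protocol 3.0 lists two items under Primary Objective: time to fitness for discharge, and "Incidence of hypoxemia in the PACU before and after intervention as defined by documentation oxygen saturation below 90" percent. The endpoint lists in protocol 3.0, protocol 10.0 and the SAP attach the primary label only to the first: "PACU Discharge Time (primary endpoint".

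**Intervals.** Both documents report 95% confidence intervals. Neither mentions Holm.

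**The concern.** With two primary outcomes, a fixed 0.025 for each is the simplest way to hold the family at 5%, but not the most efficient. Holm compares the smaller p-value with 0.025 and, if it passes, the other with 0.05. Under the protocol's rule, a second primary with p between 0.025 and 0.05 is declared negative even when the first has passed; Holm would allow that claim at the same familywise error. A result positive on both outcomes could therefore be reported as positive on one.

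The SAP errs the other way. If both outcomes are primary, testing each at 0.05 leaves the familywise error uncontrolled at 5%. The threshold sentence has to be reconciled between the documents in any case, so the choice of rule can be made then.

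**Working it through.** **Inputs.** From protocol 26.0: "we observed an overall average PACU discharge time of 152.54 minutes (SD=623.86"; n = 13,277 (Table 2) or 13,127 (Table 1) per period; SpO2 below 90% in 574/12,467 = 4.6%; 90% power; post period about the same size as the pre period. Sidedness is not stated; two-sided tests reproduce the figures. The correlation between the outcomes is not given, so 0, 0.3 and 0.6 are assumed.

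**1. The plan's own figures.** Detectable difference = (z for alpha + z for power) × SD × √(2/n).
- Alpha 0.025, n = 13,277: (2.2414 + 1.2816) × 623.86 × √(2/13,277) = 26.97 min. With n = 13,127 it is 27.13. Stated: 27.04.
- Alpha 0.05, n = 13,277: (1.9600 + 1.2816) × 623.86 × √(2/13,277) = 24.82 min. Stated: 24.84.
- SpO2 below 90%, pooled two-proportion test, 4.6% against 3.7%, n = 12,467, alpha 0.025: z = (0.009 − 2.2414 × 0.002526) / 0.002526 = 1.32, so power is 90.7%. Solved for 90% power from 574/12,467, the detectable rate is 3.71% at 0.025 (stated 3.7%). At 0.05 it is 3.78% with n = 12,467 and 3.81% with n = 13,277 (stated 3.8%).

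Both sets of figures reproduce, each at its own alpha.

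**2. Familywise error, independent outcomes.**
- Protocol rule: 1 − 0.975² = 4.94%.
- SAP rule: 1 − 0.95² = 9.75%.
- Holm: if both nulls are true, a first false rejection needs a p-value below 0.025, so the error is at most 0.025 + 0.025 = 5%. If one null is true, it can be rejected only with p below 0.05. Neither step uses the correlation.

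**3. Power with both effects at design size, correlation 0.** An outcome with 90% power at 0.025 has power Φ(2.2414 + 1.2816 − 1.9600) = Φ(1.563) = 94.1% at 0.05. The chance that its p-value falls between the two thresholds is therefore 4.1%.
- Per outcome: Bonferroni 90%; Holm 0.90 + 0.90 × 0.041 = 93.7%.
- Both: Bonferroni 0.90² = 81.0%; Holm 0.81 + 2 × 0.90 × 0.041 = 88.4%.
- At least one: 1 − 0.10² = 99.0% under either rule.

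**4. Correlated outcomes** (bivariate normal simulation, 2,000,000 draws).

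| Correlation | Each: Bonferroni → Holm | Both: Bonferroni → Holm | At least one, either rule |
|---|---|---|---|
| 0 | 90.0% → 93.7% | 81.0% → 88.4% | 99.0% |
| 0.3 | 90.0% → 93.3% | 82.2% → 88.9% | 97.8% |
| 0.6 | 90.0% → 92.9% | 83.9% → 89.7% | 96.1% |

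**5. Only one effect real, correlation 0.** Its power moves from 90.0% to 0.90 + 0.025 × 0.041 = 90.1%.

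**6. Against the SAP rule, correlation 0.** Testing both at 0.05 gives 94.1% per outcome and 0.941² = 88.5% for both. Holm gives 93.7% and 88.4%. Holm is slightly stricter, but it restores the 5% bound.

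**The case against.** **Bonferroni is valid, prespecified and budgeted for.** This stands. Protocol 26.0 sets its detectable effects at 0.025, and the arithmetic confirms 90% power for each outcome at about 13,000 patients per period. A reader might infer that the plan gives power away for nothing. The documents do not support that: planned power is not short, the gain needs both effects to be real, no requirement to win on both is stated, and Bonferroni has simple matching intervals. That last advantage counts for little here, because the plan reports 95% rather than 97.5% intervals.

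**Not all of the plan splits alpha.** This also stands. A reader might take the 0.025 rule as the rule of the whole plan, but the SAP does not use it. Against the SAP's 0.05, Holm is a tightening, so the power gain is measured against the protocol only.

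**The family may hold only one outcome.** The endpoint lists label PACU time alone as primary. If that is the intention, neither Bonferroni nor Holm is needed for it. The point therefore depends on both outcomes staying primary.

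**The rule needs exactly two p-values.** Protocol 25.1 gives each outcome a matched-sample model and a segmented regression with level and slope changes, all with p-values. It also describes the respiratory outcome first as a duration and then as binary. Until one test per outcome is named, no two-outcome rule, Bonferroni included, secures 5%. This shapes the fix but does not remove Holm's advantage.

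**Sample size matters more.** Protocol 3.0 and 7.0 put the prospective phase at about 6,500. Power at 0.025 is then about 73% for 27.04 min (13,127 against 6,500) and 75-76% for 4.6% to 3.7% (12,467 against 6,500). That is a larger loss than the choice between Bonferroni and Holm, but a separate issue.

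**Conclusion.** The point holds as a conditional recommendation. If PACU discharge time and SpO2 below 90% are both primary, Holm is at least as powerful as the protocol's fixed split at the same 5% bound, and it is a valid substitute for the SAP's unadjusted rule.

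The gain is about 3 to 4 percentage points per outcome and about 6 to 7 points for winning on both. It rests on both effects being real, 90% power each at 0.025, and a correlation between 0 and 0.6, which is assumed. Nothing is gained in the chance of at least one success, and about 0.1 point if only one effect is real. The more pressing part is the disagreement between documents: 4.94% against 9.75% familywise error for independent outcomes, depending on which one is followed.

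**What to change.** 1. State in both documents whether the primary family holds one outcome or two, and make the objectives and endpoint lists agree.
2. For each primary outcome, name the one confirmatory test, and say whether the respiratory outcome is the binary one or a duration.
3. If there are two primaries, replace the threshold sentences in protocol 25.1 and SAP, Statistical Methods, and apply the new one to the prospective analysis (protocol 25.2 and its SAP counterpart) as well: *Within each phase the two primary outcomes are tested by Holm's procedure at family alpha 0.05 (smaller p against 0.025; if significant, the other against 0.05).*
4. Keep 27.04 min and 3.7% as the worst-case detectable effects for about 13,000 patients per period. Align the SAP power text and the last row of Table 2 with them. Correct the sentence in protocol 26.0 that presents 3.7% as a difference obtained from 4.6% minus 3.8%.
5. Say how the reported intervals relate to the tests.

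The cost is a few lines of text, with no extra patients or data. The one drawback is that simultaneous intervals matching Holm are less simple than Bonferroni 97.5% intervals. The change should be made before outcome results are seen.

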25.2 Prospective analysis

The prospective analysis will largely follow a similar framework however we will focus on the primary and secondary outcomes as described above and will use a one year period prior to implementation as our baseline.

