12.0 ELIGIBILITY CRITERIA

12.1 Inclusion Criteria

One or more of the following:

1	Undergoing surgery at RR OR, SM OR
2	Obstructive or restrictive lung disease in EMR
3	Obstructive sleep apnea
4	Preoperative O2 saturation <95% (average/median of 12 hours before surgery)
5	BMI > 40
6	Acute respiratory infection within 1 month prior to surgery
7	Previous history of airway pathology

Two or more of the following:

1	BMI>35
2	Multiple intubation attempts
3	Surgical duration >2 hours
4	Upper abdominal surgery, intrathoracic surgery, or airway/head&neck surgery
5	Most recent Hb (within 6 months only) <10

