26.0 ESTIMATED SAMPLE SIZE

Sugammadex was introduced into clinical practice at UCLA in May of 2016, thus we have well more than one year of data prior to and after sugammadex introduction. As a result, the power analysis and sample size discussion is roughly the same for the retrospective and prospective portions of this study.

Over the previous one year period, approximately 13,000 patients received general anesthesia with the use of either rocuronium or vecuronium. Given that our surgical volumes are stable we would expect the sample size for the prospective portion of our study to be roughly the same. The table below contains the risk stratification for this group.

To determine the study power, we analyzed the incidence of the primary and secondary outcomes for our historical population. Because there is no current pathway, we are unable to explicitly model the power for performance of identified best practices however the power for the primary outcome as well as secondary outcomes were calculated.

In order to determine our power for the study variables patients were separated into low, medium, and high-risk groups. Low risk patients were those who had no prior documentation of OSA or respiratory disease prior to surgery. Medium risk patients were those with either OSA or respiratory disease and high risk patients were those with both diseases. It is important to note that this classification is significantly simplified as compared to the analysis that will be performed for either the retrospective or prospective studies as it fails to account for key factors such as severity of illness. Nonetheless we believe that these simplifications have the effect of underestimating the potential power and thus the below serves as a conservative estimate.

Table 1. Number of patients in low, medium, and high risk groups from 12/2017- 11/2018	
Risk Class	Number of Patients
Low – No disease	9730
Medium – OSA or Respiratory Disease	2952
High – OSA and Respiratory Disease	445
Total	13,127

Note: The risk classifications above are simplified versions of the true risk classifications to be used in the actual study

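### With one baseline year and no season term, the prospective segmented regression can mistake an annual cycle for an immediate effect of the pathway

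*Combined protocol and SAP*

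**What the plan says.** Protocol section 25.2 defines the prospective analysis by reference: "The prospective analysis will largely follow a similar framework", with attention to the primary and secondary outcomes, and it "will use a one year period prior to implementation as our baseline". The SAP repeats this under Statistical Methods. Section 26.0 puts the intervention period at one year, with study drug for "no more than 6,500 patients for the one year intervention time".

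The framework being carried over is in section 25.1 and the SAP. It has two parts. One is a propensity-matched pre/post comparison. For the other, the SAP states: "An interrupted time-series (also known as segmented regression) analysis as described by Wagner will be conducted for each outcome". Section 25.1 gives its purpose: "to estimate the pre-intervention time trend, immediate impact of intervention (change-point), as well as reliably estimating the slope change after the intervention". Estimates from both parts are reported with p-values and 95% confidence intervals. Neither document mentions a season, calendar-month or harmonic term, or a concurrent comparison series.

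The stated power (section 26.0 and the SAP) is for a two-sample t-test and a chi-square test of one year against one year. It does not cover the segmented regression.

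**The concern.** Twelve monthly points cannot separate a straight-line trend from one turn of an annual cycle. If the cycle is falling through go-live, the line fitted to each year slopes in a way that the data as a whole do not, and the two lines fail to meet at go-live. The gap is reported as the level change, which the plan interprets as the immediate effect of the intervention.

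Some seasonality is plausible from the plan itself, since one qualifying risk factor is "Acute respiratory infection within 1 month prior to surgery". That infections vary by season is an inference and is not stated in the documents. The segmented regression is also the only planned analysis that models a time trend, so readers will turn to it to judge whether a before/after difference is more than drift.

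**Working it through.** **The plan's own figure.** Section 26.0 gives 27.04 minutes as the detectable reduction in PACU discharge time. With SD 623.86, n = 13,277 per year (Table 2), two-sided alpha 0.025 and 90% power: 623.86 × (2.241 + 1.282) × √(2/13,277) = 26.97 minutes. The figure reproduces closely. The SpO2 below 90% figure (4.6% to about 3.7%, a drop of 0.9 points) reproduces too. Both describe whole-year comparisons.

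**Size of the false level change.** Take 12 monthly points on each side of go-live and a noise-free annual cosine of amplitude A. Fit an intercept, trend, level change and slope change by least squares. Both years contain the same full cycle, so the fitted lines have the same slope b and the same mean and are centred 12 months apart. Hence the gap at go-live is −12b and the slope change is 0.

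- Go-live at peak or trough: b = 0, gap 0.
- Go-live one or two months from peak or trough: gap 0.97A or 1.68A in absolute size.
- Go-live three months from either: b = ∓0.162A, gap ±12 × 0.162A = ±1.95A.
- Root mean square over all go-live times: 1.38A.
- Difference between the two whole-year means: 0 in every case.

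**False-positive rate, SpO2 below 90%.** Inputs: p = 574/12,467 = 4.6%; alpha 0.025 from section 25.1, critical value 2.24. Assumptions: monthly points, independent residuals, equal patient numbers in both years. The least-squares variance factor for the level change at go-live is 0.670.

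- SE at 12,467 a year: 100 × √(0.0460 × 0.9540 × 0.670 / (12,467/12)) = 0.53 points.
- SE at 6,500 a year: 0.74 points.
- Rejection rate for a gap g: Φ(g/SE − 2.24) + Φ(−g/SE − 2.24).

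The amplitude is assumed:

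| Amplitude (points) | Worst gap (points) | 12,467 a year: average / worst | 6,500 a year: average / worst |
|---|---|---|---|
| 0.25 | 0.49 | 6% / 9% | 4% / 6% |
| 0.5 | 0.97 | 18% / 34% | 10% / 18% |
| 1.0 | 1.95 | 54% / 92% | 35% / 65% |

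The nominal rate is 2.5%. The worst gap at 0.5 points is about the size of the 0.9-point drop used for planning. With a baseline year near 12,467 and an intervention year near 6,500, the SE lies between the two values.

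**PACU discharge time.** An assumed amplitude of 10% of the mean gives a worst gap of 0.10 × 152.54 × 1.945 = 29.7 minutes. The SE is about 15.4 minutes at 13,277 a year, so the worst-case rejection rate is 38%.

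**Candidate remedies** (SE for SpO2 below 90% at 12,467 a year, same formula with the variance factor of each design):

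| Baseline months | Season terms | Variance factor | SE (points) | Worst false level, pure cycle |
|---|---|---|---|---|
| 12 | none | 0.670 | 0.53 | 1.95A |
| 12 | one harmonic pair | 1.514 | 0.80 | 0 |
| 24 | none | 0.502 | 0.46 | 1.46A |
| 18 | one harmonic pair | 0.694 | 0.54 | 0 |
| 24 | one harmonic pair | 0.673 | 0.53 | 0 |

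Calendar-month terms on 12 + 12 months make time an exact combination of the month and post indicators (rank 14 of 15 columns), so the level change cannot be estimated.

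The zeros hold because the input was a pure cycle. For a three-month winter pulse on 12 + 12 months, the worst false level is 1.13 pulse heights without a harmonic pair and 1.36 with one. The same fit on 18 or 24 baseline months leaves 0.50 or 0.55 with one pair and 0.19 or 0.21 with two.

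**The case against.** Several objections carry weight. Section 25.2 does not restate the segmented regression; its use in the prospective part rests on the framework being largely similar. Only the quantities to be estimated are listed, with a methods paper cited, so the absence of a season term means that none is mentioned, not that one is ruled out. Still, section 25.2 changes only the outcomes and the baseline window, and carrying the model over is the natural reading.

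The matched comparison of whole years is balanced for a stable cycle, it carries the stated power, and nothing names the level change as the primary test. That stands. A reader might infer that season undermines the study's main before/after result, but the documents do not support this.

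The 12,467 patients behind the larger rates are all comers, mostly low risk (9,841 of 13,277 in Table 2), and were not selected on recent infection. The rates at about 6,500 a year, the planned prospective size, are lower and at a small amplitude close to nominal. That also stands.

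The statement in section 26.0, "thus we have well more than one year of data prior to and after sugammadex introduction", concerns the introduction of sugammadex. It shows that earlier data exist, not that a one-year baseline is an error in itself.

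**Conclusion.** The point holds for one term of one analysis: the level change in the prospective segmented regression. An annual cycle can appear there as an effect of the pathway, by 0 to 1.95A (root mean square 1.38A), and can favour the pathway, mask a benefit or suggest harm. Under assumed amplitudes of 0.25 to 1.0 points, the average false-positive rate runs from 4% to 54% and the worst from 6% to 92%, across the two sample sizes, against 2.5%. The result rests on monthly points, independent residuals and a stable sinusoidal cycle.

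A reader might go further and infer that a seasonal cycle will be read as an effect. The documents do not support that: they give no amplitude and no go-live month, and the bias vanishes at a peak or trough. Nor is the short baseline alone the cause. Without a season term, 24 or 36 baseline months still leave about 1.46A or 1.29A.

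**What to change.** In section 25.2 and the SAP, make one joint change, for the segmented regression only:

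- State explicitly that the prospective analysis includes the segmented regression.
- Run the pre-implementation series over all usable warehouse months after the sugammadex learning-curve year: at least 18, preferably 24 or more. Introduction in May 2016 (section 26.0) plus the excluded year (section 6.0) leaves about 18 months by November 2018, the end of the Table 1 window.
- Add a 12-month sine and cosine pair. As a sensitivity analysis, add a second harmonic or calendar-month terms, because one pair does not fully absorb a short winter peak.
- Keep the one-year window for the matched comparison.

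The season term should not be added to 12 + 12 months alone. There, calendar-month terms are not estimable, and a harmonic pair raises the SE by about 50% (0.53 to 0.80 points) without removing bias from a short peak.

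A concurrent series of patients who do not meet the risk criteria would be a natural support, but it is not available as the plan is written. Section 12.1 lists surgery at these operating rooms as a qualifying criterion in its own right, and section 26.0 extends the pathway to some low-risk patients.

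The cost is SAP wording and a longer extract from the existing warehouse, with no new patients or procedures. With 18 to 24 baseline months and one harmonic pair the SE is 0.53 to 0.54 points, about the same as now, though slightly wider than the longer series would give without the season term (0.46 at 24 months).
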